1.2 Overall Rationale for the Study

This is a parallel-group long-term extension (LTE) trial of studies CNTO136ARA3002 and CNTO136ARA3003 to assess the long-term safety and efficacy of sirukumab in subjects with moderately to severely active RA. Subjects who have completed participation in studies CNTO136ARA3002 or CNTO136ARA3003 will be eligible to enroll in this study. Subjects are to continue to receive the identical sirukumab SC dose regimen of 100 mg every 2 (q2) weeks or 50 mg every 4 (q4) weeks that they were receiving upon completion of participation in studies CNTO136ARA3002 and CNTO136ARA3003.

Following the database lock for the primary endpoint, analysis of CNTO136ARA3002 and CNTO136ARA3003 PK and efficacy data showed that there was no clear dose response between the sirukumab SC 50 mg q4 weeks and sirukumab SC 100 mg q2 weeks dose groups across efficacy endpoints. Furthermore, there were a greater proportion of subjects with hypersensitivity reactions and injection site reactions in the sirukumab 100 mg q2 weeks dose group compared with the sirukumab 50 mg q4 weeks dose group. Therefore, to allow for minimization of the exposure to this immunosuppressant biologic agent, subjects treated with SC sirukumab 100 mg q2 weeks will be offered the option to reduce the sirukumab dose to 50 mg q4 weeks at the investigator's discretion after the study becomes open-label. This decision can be made at the subject's first or second major resupply visit (up until approximately 7 months) after implementation of Amendment 3 at the study site. Once a subject's dose is reduced to 50 mg q4 weeks, the subject will receive that dose for the remainder of the trial (ie, a return to 100 mg q2 weeks will not be allowed). If a subject opts to remain on the sirukumab 100 mg q2 weeks dose, he or she will remain on that dose for the duration of their participation in the study (ie, the subject will not have the option to reduce the dose at a subsequent timepoint).

Additionally, a substudy of enrolled subjects in CNTO136ARA3004 will further assess the usability of the SmartJect™ Autoinjector (PFS-AI).

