5.2 Blinding

To maintain the study blind, the study agent container will have a multipart label with directions for use and other information, but not the identity of the study agent, on each part. One part of the label is designed to be torn off, separated from the study agent container, and attached to the subject's source documents. The rest of the label will remain affixed to the study agent container. Thus, the study agent assigned to a subject will be linked between the container and the subject without breaking the study blind. The study agent kit number will be entered in the electronic case report form (eCRF) or other equivalent data capture method when the drug is administered.

CNTO 136 (sirukumab): Clinical Protocol CNTO136ARA3004 – Amendment 3

The investigator will not be provided with treatment codes, but the codes will be maintained within the IVRS/IWRS, which has the functionality to allow the investigator to break the blind for an individual subject when there is a need based on medical judgment.

The study will remain blinded until the following 3 conditions have been met: the Week 52 DBL occurs in study CNTO136ARA3002, the Week 24 DBL occurs in study CNTO136ARA3003, and the last AI usability substudy subject completes the Week 16 visit or terminates from the study.

The blind should be broken only if specific emergency treatment/course of action would be dictated by knowing the treatment status of the subject. In such cases, the investigator may determine the identity of the treatment from the IVRS/IWRS provider. It is strongly recommended that the investigator contact the Sponsor or its designee if possible to discuss the particular situation prior to unblinding in IVRS/IWRS. Telephone contact with the Sponsor or its designee will be available 24 hours per day, 7 days per week. In the event the blind is broken, the Sponsor must be informed as soon as possible. The date and reason for the unblinding must be documented in the appropriate section of the eCRF, and in the source document. The documentation received from the IVRS/IWRS indicating the code break must be retained with the subject's source documents in a secure manner (eg, sealed envelope) so as not to unblind the treatment assignment to the subject, the study site, or Sponsor personnel. The investigator is also advised not to reveal the study treatment assignment to the subject, the study site, or Sponsor personnel.

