6.2 Blinding

To maintain the blind, all subjects will receive study agent as 1 SC injection as follows:

Group 1 (sirukumab 100 mg): 1.0 mL sirukumab 100 mg injection q2 weeks.

Group 2 (sirukumab 50 mg): 1.0 mL sirukumab 50 mg injection q4 weeks. Between sirukumab injections, placebo SC injections will be administered at Weeks 2, 6, and q4 weeks until the study becomes open-label and placebo injections will be discontinued.

After the study becomes open-label, subjects treated with SC sirukumab 100 mg q2 weeks will be offered the option to reduce the sirukumab dose to 50 mg q4 weeks at the investigator's discretion. This decision can be made at the subject's first or second major resupply visit (up until approximately 7 months) after implementation of Amendment 3 at the study site.

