Subjects at selected sites in the US will be offered the opportunity to consent to join a secure, web-based platform managed by a third party vendor so that they may access results to select clinical laboratory tests collected during the study (as defined above with the exception of RBC count). More details will be provided in the Informed Consent Form for these subjects.

Pathology

If a subject requires tissue sampling for the evaluation of an adverse event, the Sponsor may request that the sample be sent for additional central evaluation.

Vital Signs

Blood pressure and body weight will be measured.

Physical Examination

A general physical examination will be performed as indicated in [Table 1](#). Clinically significant findings should be reported as AEs.

Allergic Reactions

All subjects will be observed carefully for symptoms of allergic reactions for at least 30 minutes after the SC injection of study agent at the study site at least until the study becomes open-label. If mild or moderate allergic reaction is observed, acetaminophen 650 mg PO or NSAIDS and diphenhydramine 25 mg PO or IV may be administered. If the reaction is not severe, subsequent injections at the appropriate treatment intervals may be undertaken with caution. Subjects who self-inject the study agent away from the study site will receive detailed instructions on how to monitor and report AEs.

Subjects with severe reactions following an injection such as bronchospasm with wheezing and/or dyspnea requiring ventilator support, or symptomatic hypotension with a decrease in

systolic blood pressure greater than 40 mm Hg will not be permitted to receive any additional study agent injections. In the case of such reactions, appropriate medical treatment should be administered.

Injection Site Reactions

An injection site reaction is any unfavorable or unintended sign that occurs at the study agent injection site. All subjects must be carefully observed for symptoms of an injection site reaction. Subjects will be observed for at least 30 minutes after the SC injection of study agent for symptoms of an injection-site reaction at least until the study becomes open-label. If an injection site reaction is observed, the subject should be treated at the investigator's discretion. Any adverse reaction (eg, pain, erythema, and/or induration) should be noted on the AE page of the eCRF.

Early Detection of Active Tuberculosis

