11.8 Safety Analyses

Adverse Events

The verbatim terms used in the eCRF by investigators to identify AEs will be coded using the MedDRA dictionary. All reported AEs with onset during the treatment phase (ie, treatment-emergent AEs and AEs that have worsened since baseline) will be included in the analysis. For each AE, the percentage of subjects who experience at least 1 occurrence of the given event will be summarized by treatment group. Other safety analyses include the proportion of subjects with infections, SAE, AE leading to discontinuation.

Summaries, listings, datasets, or subject narratives may be provided, as appropriate, for those subjects who die, who discontinue treatment due to an AE, or who experience a severe or a serious adverse event (SAE).

Additional analyses will be performed for the number of subjects with cardiovascular SAEs by cardiovascular type and the number of subjects with malignancies by malignancy type (eg, lymphoma, nonmelanoma skin cancers, and other malignancies).

Clinical Laboratory Tests

Laboratory data will be summarized by type of laboratory test. NCI-CTCAE grades will be used in the summary of laboratory data. For some laboratory data, which are not covered in the NCI-CTCAE grading criteria, shift tables and/or other abnormal cutoff levels may be used for summaries. Descriptive statistics will be calculated for selected laboratory analyte at baseline and at each scheduled time point. A listing of subjects with post-baseline abnormal laboratory results based on NCI-CTCAE grades will also be provided.

Vital Signs

The proportion of subjects with markedly abnormal post-baseline values will be summarized.

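### Section 11.8 counts injection-site reactions to blinding-only placebo injections against 50 mg q4 weeks, to a degree that depends on each subject's blinded time

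*Protocol*

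**What the plan says.** Protocol Section 11.8 sets the general rule: "For each AE, the percentage of subjects who experience at least 1 occurrence of the given event will be summarized by treatment group". Section 11 splits the analyses by parent study and treatment group. Neither section mentions a split by blinded and open-label phase, a rate per injection, or a separate analysis of injection-site reactions.

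Section 9.8 brings these reactions under that rule. It defines them broadly ("An injection site reaction is any unfavorable or unintended sign that occurs at the study agent injection site") and sends them to the adverse event page ("Any adverse reaction (eg, pain, erythema, and/or induration) should be noted on the AE page of the eCRF"). Study agent here includes the blinded placebo supplies (Sections 5.2, 6.2 and 14.1).

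The injection schedule is in Section 6.2:

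- "Group 1 (sirukumab 100 mg): 1.0 mL sirukumab 100 mg injection q2 weeks".
- In the other group, the active injection is 50 mg, once every 4 weeks.
- For Group 2 only: "Between sirukumab injections, placebo SC injections will be administered at Weeks 2, 6, and q4 weeks until the study becomes open-label".

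Section 5.2 ends blinding when three study-level conditions are met, so blinded time differs by entry date. After that, Section 6.1 lets Group 1 subjects reduce to 50 mg q4 weeks. Among the reasons for that option, Section 1.2 says that in the primary studies "there were a greater proportion of subjects with hypersensitivity reactions and injection site reactions in the sirukumab 100 mg q2 weeks dose group".

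**The concern.** Group 2's placebo injections are not part of the 50 mg q4-week regimen. They exist only to match Group 1's injection frequency while treatment is masked. A needle and 1.0 mL of placebo solution can still cause pain or erythema, and under Section 11.8 such a reaction counts for Group 2 exactly as a reaction to sirukumab would.

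The placebo injections stop at open-label. Group 2's percentage therefore mixes time with and without them, in proportions set by the blinding calendar. It describes neither the regimen as given open-label nor a risk per injection.

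These reactions are part of the protocol's stated reason for offering dose reduction, and this study supplies the long-term data on them. A reader comparing the two groups could not tell how much of Group 2's figure came from the masking scheme.

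**Working it through.** The protocol states no reaction rate to reproduce, so the check has two steps: count injections from the schedule, then show what the summary rule does under stated assumptions.

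**Injection counts** (Sections 6.1 and 6.2; Week 0 excluded because it is the last dose of the primary study)

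- Group 1 at q2 weeks: 52/2 = 26 sirukumab injections a year.
- Group 2, blinded: 52/4 = 13 sirukumab plus 13 placebo, 26 in all.
- Group 2, open-label: 13 sirukumab.

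**Assumptions, none from the documents:** risk p per sirukumab injection; risk p0 per placebo injection; independent injections; full adherence.

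The chance of at least one reaction in a Group 2 blinded year is 1 − (1 − p)^13 × (1 − p0)^13. In an open-label year it is 1 − (1 − p)^13.

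With p = 0.5%:

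| Placebo risk | Blinded year | Open-label year |
|---|---|---|
| p0 = 0 | 1 − 0.995^13 = 6.3% | 6.3% |
| p0 = 0.25% | 1 − 0.995^13 × 0.9975^13 = 9.3% | 6.3% |
| p0 = 0.5% | 1 − 0.995^26 = 12.2% | 6.3% |

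For other values of p, the blinded-year range from p0 = 0 to p0 = p is 1.3% to 2.6% at p = 0.1%, and 12.2% to 23.0% at p = 1%.

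**Dependence on blinded time.** Blinded duration is also not given, so take 0, 16, 52 and 104 weeks. Through Week 156, Group 2 has 156/4 = 39 sirukumab injections, plus 0, 4, 13 or 26 placebo injections. At p = 0.5%:

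| Blinded weeks | Injections | Group 2, p0 = p | Group 2, p0 = 0 |
|---|---|---|---|
| 0 | 39 | 17.8% | 17.8% |
| 16 | 43 | 19.4% | 17.8% |
| 52 | 52 | 22.9% | 17.8% |
| 104 | 65 | 27.8% | 17.8% |

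Dose, drug and risk per sirukumab injection are the same in every row. The gap between the last two columns is the placebo contribution, from none to 10.0 percentage points across these assumptions.

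**Direction.** The placebo contribution can only raise Group 2's figure. Group 1 has no placebo injections.

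**The case against.** Several counter-arguments are strong, and some of them stand.

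- **Fewer injections is not a bias.** A reader might infer that halving Group 2's injections at open-label unfairly favours 50 mg q4 weeks. The treatment groups are regimens (Sections 5.1 and 11), and a lower injection count belongs to the q4-week regimen. Percent of subjects is a valid measure of it. This stands in full.
- **No general ratio between groups follows.** Equal risk for every injection gives 12.2% against 6.3% in an open-label year, a ratio of about 1.9, and a reader might take that as the size of the problem. It is not. It is the regimen difference just described, and it assumes that every Group 1 subject stays at 26 injections a year. If half reduced dose throughout that year and were still counted in Group 1 (an assumption), Group 1 would show about (12.2% + 6.3%)/2 = 9.3%.
- **The placebo effect may be small.** With no placebo risk it vanishes. If reactions cluster in a few susceptible subjects, percent with at least one depends less on injection count. After Week 2, all visits in Table 1 fall on multiples of 4 weeks, so Group 2's placebo injections nominally fall between visits. For home injectors, their reactions reach the database mainly by self-report.
- **Hypersensitivity cannot be attributed the same way.** Section 3.2.3 equates about 16 weeks with at least 5 half-lives, which allows a half-life of up to 16/5 = 3.2 weeks. Sirukumab may still be present at a placebo injection, so assigning a reaction to the most recent injection could mislabel it.
- **The consequence is limited.** The study is descriptive, the groups are not randomised here, and these reactions are neither primary nor major secondary endpoints. The SAP text was not available for this review and may already contain such a table.

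None of this removes the narrow point: the protocol's stated rule mixes reactions to masking injections into Group 2's figure and does not show how many there are.

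**Conclusion.** The point holds for injection-site reactions, as a modest weakness in a descriptive safety summary. It affects no error rate and no hypothesis test.

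That reactions to blinding-only injections count for Group 2, and that they stop at open-label, follows directly from Sections 6.2, 9.8 and 11.8. The size does not follow from the documents. At an assumed 0.5% per sirukumab injection, the inflation of a Group 2 blinded year is between zero and 5.9 percentage points (12.2% − 6.3%), depending on placebo risk, with independent injections and full adherence.

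Two features make a phase split more useful still. Section 9.8 requires the 30-minute observation after injection only until open-label, so ascertainment may change at the same time as the injection count. Group 1 subjects who reduce dose also halve their injections, and the protocol does not say where their later reactions are counted.

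**What to change.** Add the following to Section 11.8, or confirm that the SAP already provides it:

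1. Report injection-site reactions separately for the blinded and open-label phases. For Group 1, separate time before and after dose reduction.
2. Report injection-site reactions per 100 sirukumab injections and, separately, per 100 placebo injections, linking each reaction to an injection by kit number and administration date.
3. Report hypersensitivity reactions by phase only, without attributing them to the most recent injection.
4. Keep percent of subjects with at least one reaction as the regimen-level measure.

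The data are already collected: kit numbers in the eCRF (Section 5.2), administration logs (Section 7) and the patient diary for home injections (Section 17.4). Visits and treatment do not change. The cost is one extra descriptive table with its programming. The limitation is that dates and reactions for home injections rest on the diary and self-report, so the table should say so.

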11.9 Interim Analysis

No formal interim analyses are planned, though analyses based on interim releases and locks may be carried out for integrated PK, immunogenicity, safety and efficacy data.

11.10 Data Monitoring Committee

An independent DMC will be established to monitor data on an ongoing basis to ensure the continuing safety of the subjects enrolled in this study. The committee will meet periodically to review interim data. After the review, the DMC will make recommendations regarding the continuation of the study.

The DMC will have 3 to 6 members who are independent of the Sponsor. None of the members will be participating in the current study. The DMC will consist of at least 1 medical expert in the relevant therapeutic area and at least 1 statistician. The members of the committee will be specified prior to study initiation. The major function of this committee will be to monitor the safety of the study agent and to provide recommendations for placing the study on hold or stopping the study in the event that any unanticipated serious events occur.

The DMC will conduct periodic safety reviews that will occur every 4 months until at a minimum, the study becomes open-label. The DMC may change the frequency or number of reviews based on interim safety findings. The safety reviews will focus on particular AEs, SAEs, and mortality.

SAE reports will be provided to the DMC members on an ongoing basis. The DMC will have access to unblinded data and review tabulated safety summaries (if appropriate) and any additional data that the DMC may request during the conduct of the study. No formal statistical hypothesis testing is planned. In addition, during the study, the Sponsor's study responsible physician (or designee) will regularly review blinded safety data from the sites and notify the DMC and appropriate Sponsor personnel of any issues.

The content of the safety summaries, the DMC role and responsibilities, and the general procedures (including communications) and their recommendations on the study conduct will be defined and documented in the DMC charter prior to the first DMC review.

11.11 Clinical Events Committee

The CEC is an independent committee composed of external specialists, blinded to treatment assignment, which will be commissioned to review case information on serious CV events (myocardial infarction, stroke, death, hospitalization for angina, hospitalization for TIA). The operations, processes, and definitions to be employed by the committee will be defined in the CEC charter.

12 ADVERSE EVENT REPORTING

Timely, accurate, and complete reporting and analysis of safety information from clinical studies are crucial for the protection of subjects, investigators, and the Sponsor, and are mandated by regulatory agencies worldwide. The Sponsor has established Standard Operating Procedures in conformity with regulatory requirements worldwide to ensure appropriate reporting of safety information; all clinical studies conducted by the Sponsor or its affiliates will be conducted in accordance with those procedures.

12.1 Definitions

12.1.1 Adverse Event Definitions and Classifications

Adverse Event

An adverse event is any untoward medical occurrence in a clinical study subject administered a medicinal (investigational or non-investigational) product. An adverse event does not necessarily have a causal relationship with the treatment. An adverse event can therefore be any unfavorable and unintended sign (including an abnormal finding), symptom, or disease temporally associated with the use of a medicinal (investigational or non-investigational) product, whether or not related to that medicinal (investigational or non-investigational) product. (Definition per ICH)

This includes any occurrence that is new in onset or aggravated in severity or frequency from the baseline condition, or abnormal results of diagnostic procedures, including laboratory test abnormalities.

Note: The Sponsor collects adverse events starting with the signing of the ICF (see Section 12.3.1, All Adverse Events, for time of last adverse event recording).

Serious Adverse Event

A SAE based on ICH is any untoward medical occurrence that at any dose:

- Results in death
- Is life-threatening
(The subject was at risk of death at the time of the event. It does not refer to an event that hypothetically might have caused death if it were more severe.)
- Requires inpatient hospitalization or prolongation of existing hospitalization
- Results in persistent or significant disability/incapacity
- Is a congenital anomaly/birth defect
- Is a suspected transmission of any infectious agent via a medicinal product
- Is medically important*

*Medical and scientific judgment should be exercised in deciding whether expedited reporting is also appropriate in other situations, such as important medical events that may not be immediately life threatening or result in death or hospitalization but may jeopardize the subject or may require intervention to prevent one of the other outcomes listed in the definition above. These should usually be considered serious.

Unlisted (Unexpected) Adverse Event/Reference Safety Information

An adverse event is considered as unlisted, if the nature or severity is not consistent with the applicable product reference safety information. For an investigational product, the

CNTO 136 (sirukumab): Clinical Protocol CNTO136ARA3004 – Amendment 3

expectedness of an adverse event will be determined by whether or not it is listed in the Investigator's Brochure.

Adverse Event Associated with the Use of the Drug

An adverse event is considered associated with the use of the drug if the attribution is possible, probable, or very likely by the definitions listed in Section 12.1.2.

12.1.2 Attribution Definitions

Not Related

An adverse event that is not related to the use of the drug.

Doubtful

An adverse event for which an alternative explanation is more likely, eg, concomitant drug(s), concomitant disease(s), or the relationship in time suggests that a causal relationship is unlikely.

Possible

An adverse event that might be due to the use of the drug. An alternative explanation, eg, concomitant drug(s), concomitant disease(s), is inconclusive. The relationship in time is reasonable; therefore, the causal relationship cannot be excluded.

Probable

An adverse event that might be due to the use of the drug. The relationship in time is suggestive (eg, confirmed by dechallenge). An alternative explanation is less likely, eg, concomitant drug(s), concomitant disease(s).

Very Likely

An adverse event that is listed as a possible adverse reaction and cannot be reasonably explained by an alternative explanation, eg, concomitant drug(s), concomitant disease(s). The relationship in time is very suggestive (eg, it is confirmed by dechallenge and rechallenge).

